2.7.1 Secondary endpoints

The following analyses Changes in platelet count, hemoglobin and neutrophil count, Duration of hematological response, Maximum duration of Platelet and RBC transfusion independence will be generated for the final CSR.

Hematological Response at Week 13 and Week 52

Hematologic response rate at Week 13 and Week 52 will also be assessed by investigator according to the International Working Group (IWG) criteria for the primary endpoints shown in the [Table 2-2](#) above.

The analysis for hematologic response rate at Week 13 will only be produced at primary analysis, and hematologic response rate at week 52 will only be produced at updated analysis.

Changes in platelet count, hemoglobin and neutrophil count

Value and changes in platelet count (in the absence of platelet transfusion), hemoglobin (in the absence of RBC transfusion) and neutrophil count (in the absence of G-CSF) will be calculated according to the lab test results entered into CRF.

Time to hematological response

Time to hematological response is defined as the time from the date of first study drug administration to the first hematological response which is defined in [Section 2.5.1](#). All subjects in the FAS will be included in the time to hematological response calculations.

These will be analyzed and plotted for four assessment criteria: Hematological Response; Platelet/Platelet Transfusion; Hemoglobin/RBC Transfusion; Neutrophils.

The analysis for time to hematological response will only be produced at primary analysis.

Duration of hematological response

For subjects who responded, duration of hematological response will be defined as the number of months from the first date of a hematological response which is defined in [Section 2.5.1](#) until the first date of a relapse (defined as not meeting the response criteria) or a death. Only subjects with at least 2 response assessments are included in the duration of response assessment. Patient still responding at the cut-off date will be censored at date of last response assessment.

These will be analyzed and plotted for four assessment criteria: Hematological Response; Platelet/Platelet Transfusion; Hemoglobin/RBC Transfusion; Neutrophils.

Frequency and amount of transfusion

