2.7.2 Statistical hypothesis, model, and method of analysis

Hematological Response at Week 13 and Week 52

The number and percentage of subjects who meet the hematological response criteria (at Week 13 and Week 52 respectively) will be presented and exact 90% confidence interval will be reported. And the number and percentage of assessment item for the hematological response criteria and for the detailed hematological response criteria will be presented.

The derived response by programming at week 13 and Week 52 will also be summarized as above.

Changes in platelet count, hemoglobin and neutrophil count

Values and changes in platelet count (in the absence of platelet transfusion), hemoglobin (in the absence of RBC transfusion) and neutrophil count (in the absence of G-CSF) will be summarized at each visit. Descriptive statistics including mean, SD, median, 25th and 75th percentiles, minimum, and maximum will be summarized for the changes.

Median and interquartile range will be plotted.

Time to hematological response

The distribution function of time to hematologic response will be estimated using the Kaplan-Meier method and will be plotted. The median time to hematologic response along with 90% CIs will be presented. If a subject does not meet hematological response before or at the cutoff date, censoring will be performed using the date of the last assessment.

Duration of hematological response

The distribution function of duration of hematologic response will be estimated using the Kaplan-Meier method and will be plotted. If the number of relapses or deaths allows, the median time to hematologic response along with 90% CIs will be presented.

Relapse-free probability will be estimated using the Kaplan-Meier method at 3 months, 6 months, 9 monthes, one year, and yearly after as well.

Frequency and amount of transfusion

The frequency and the amount of platelets transfusion in each period (Baseline: 4 weeks before Day 1; Week 13, 26, 52: 4 weeks before each visit day) will be summarized by descriptive statistics including mean, SD, median, 25th and 75th percentiles, minimum, and maximum.

Proportion of subjects with transfusion decrease

The number and percentage of subjects with platelet or RBC transfusion decrease or transfusion-free in each period will be presented.

In addition, the number and percentage of subjects with 50% platelet or RBC transfusion reduction in each period will be presented.

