2.7.3 Handling of missing values/censoring/discontinuations

Hematological Response at Week 13 and Week 52

For the analysis of hematological response at Week 52, patients who are still ongoing but have not reached the considered timepoint yet will not be included in the analysis of response at that timepoint. However, patients with a missing or 'Non-evaluable' response for other reasons will be treated as non-responders at that timepoint in the calculation of the hematological response rate.

Time to hematological response

For time to hematological response, if a subject does not meet hematological response before or at the cutoff date, censoring will be performed using the date of the last assessment.

Duration of hematological response

For duration of hematological response, patient still responding at the cut-off date will be censored at date of last response assessment.

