2.8.2 Deaths

The number and percentage of deaths occurring during the on-treatment period and at any time during the study will be provided. Deaths occurring during the on-treatment period will be further summarized by system organ class and preferred term. All deaths will be listed and flagged appropriately.

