3.1 Primary analysis

The hematologic response rate at Week 24 in the pivotal study of NIH-09-H-0154 was 40%. Assuming a same response rate (40%) in Chinese subjects, the 90% confidence interval of the hematological response rate with a total of 20 subjects will be (21.7%, 60.6%).

Below table shows the 90% CIs for various observed response rate. The maximum half-width of the 90% CIs is 19.8%.

Table 3-1 90% CIs for various observed response rate

Sample size	# of responders	Hematologic response rate (%)	90% CI (%)
20	4	20	(7.1, 40.1)
20	6	30	(14.0, 50.8)
20	8	40	(21.7, 60.6)

Sample size	# of responders	Hematologic response rate (%)	90% CI (%)
20	10	50	(30.2, 69.8)

The 12 evaluable subjects for intensive PK sampling was chosen based on feasibility and practical considerationzs to assist in characterizing the PK of eltrombopag in Chinese subjects.

4 Change to protocol specified analyses

No change from protocol specified analysis was made.

5 Appendix

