5.4.2 Key secondary analysis

Kaplan-Meier estimates

For time to event endpoints (time to response, duration of response etc..), an estimate of the survival function will be constructed using Kaplan-Meier (product-limit) method as implemented in PROC LIFETEST with METHOD=KM option.

Quartiles of the survival function, if reached, will be obtained along with 90% confidence intervals calculated from PROC LIFETEST output using the method of ([Brookmeyer and Crowley, 1982](#)). Kaplan-Meier estimates of the survival function with 90% confidence

intervals at specific time points will be summarized. The standard error of the Kaplan-Meier estimate will be calculated using Greenwood's formula ([Collett, 1994](#)).

6 Reference

1. Clopper CJ and Pearson ES (1934). The use of confidence or fiducial limits illustrated in the case of the binomial. *Biometrical*, 26, 404-413.
2. Brookmeyer R and Crowley J (1982). A Confidence Interval for the Median Survival Time. *Biometrics*, 38, 29 - 41.
3. Collet D (1994). Modelling survival data in medical research. London, Chapman & Hall.

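### Duration of response excludes a responder who dies after a single assessment, so any such death biases the relapse-free estimates upward from then on

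*SAP*

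**What the plan says.** SAP 2.7.1 measures duration from the first date of response "until the first date of a relapse (defined as not meeting the response criteria) or a death". Death is therefore an event. SAP 2.7.2 confirms this, because it makes the median depend on there being enough relapses or deaths.

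The same paragraph of SAP 2.7.1 then restricts the analysis: "Only subjects with at least 2 response assessments are included in the duration of response assessment". Protocol 12.5.1 also counts relapse and death and carries the same restriction. Neither document makes an exception for a subject who died.

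The only other handling rule is in SAP 2.7.3: "For duration of hematological response, patient still responding at the cut-off date will be censored at date of last response assessment". It does not apply to a subject who died.

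On output, SAP 2.7.2 says "Relapse-free probability will be estimated using the Kaplan-Meier method at 3 months", and goes on to 6, 9 and 12 months and every year after that. SAP 2.7.1 adds: "These will be analyzed and plotted for four assessment criteria: Hematological Response; Platelet/Platelet Transfusion; Hemoglobin/RBC Transfusion; Neutrophils". Duration of response is one of the few efficacy analyses that SAP 2.7.1 lists for the final CSR.

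**The concern.** Entry to the analysis depends on what happens after response begins, because a responder must live long enough to have a second assessment. The endpoint counts death as a failure, and the entry rule removes the earliest deaths. The loss runs in one direction, so it does not average out.

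The curves rest on few subjects. With about 20 enrolled and the assumed 40% response rate there would be about 8 responders. Each lineage curve has no more responders than the overall curve, so one removed death weighs at least as much there. The study supports registration in China, and a reader of the final CSR would take the relapse-free probabilities as applying to all responders. No estimate for all responders is planned beside them.

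**Working it through.** **Inputs.** Sample size of about 20 and response rate of 40% (SAP 3 and 3.1); responder counts 4, 6, 8 and 10 (SAP Table 3-1); events are relapse and death (SAP 2.7.1); product-limit estimate, and "The standard error of the Kaplan-Meier estimate will be calculated using Greenwood's formula" (SAP 5.4.2). The documents contain no duration data, so the figures in steps 3 to 5 are illustrations.

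**1. The plan's own figures.** SAP 3.1 says: "Below table shows the 90% CIs for various observed response rate". Exact 5% and 95% binomial limits for 4, 6, 8 and 10 of 20 give (7.1, 40.1), (14.0, 50.8), (21.7, 60.6) and (30.2, 69.8). The largest half-width is (69.8 − 30.2)/2 = 19.8. All agree with the SAP. The plan gives no comparable figure for duration.

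**2. Whom the rule can remove.**
- A responder who relapses: relapse means failing the criteria at a later assessment, so there are already two. None is removed.
- A living responder with one assessment: would be censored at duration zero. Adding such a subject leaves every estimate unchanged, so removal does no harm.
- A responder who dies after one assessment: has a defined event, which is removed.

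**3. One such death, no other event.** With n responders the estimate from the death onward is (n − 1)/n. Under the rule it is 100%.

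| Responders | Death kept | Rule as written |
|---|---|---|
| 4 | 3/4 = 75.0% | 100% |
| 6 | 5/6 = 83.3% | 100% |
| 8 | 7/8 = 87.5% | 100% |
| 10 | 9/10 = 90.0% | 100% |

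Two such deaths among 8 give 6/8 = 75.0% against 100%.

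**4. Precision, n = 8.** Greenwood standard error with the death kept: 0.875 × √(1/(8 × 7)) = 0.117, or 11.7 points. Under the rule it is 0.

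**5. Direction.** Take 8 responders, a relapse at 2.99 months and a death at 5 months after a single assessment.
- Death kept: 7/8 = 87.5% at 3 months; 7/8 × 6/7 = 75.0% at 6 months.
- Death removed (7 subjects): 6/7 = 85.7% at 3 and at 6 months.

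Before the removed death the estimate is unchanged or slightly lower; from the death onward it is higher. Without earlier censoring the inflation factor is n/(n − 1): 8/7 = 1.14 for 8 responders and 4/3 = 1.33 for 4. In 20,000 random small data sets (85,194 comparisons at or after the removed death), removal never lowered the estimate.

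**6. How assessments are counted.** The text does not say whether the two are counted in total or from first response. In total, which is the more natural reading, only a subject who responds at the very first assessment and dies before the second is lost. Counted from first response, any responder who dies before the next assessment is lost. The deletion happens under both readings; the first affects fewer subjects.

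**The case against.** The strongest reply is that this may never happen. Under the in-total reading the subject must respond at the first assessment and die before the second. The documents give no death rate for responders. The nearest figure is in Protocol 1.1: about 40% dead within 5 years among patients unresponsive to initial IST. Taken as a high-side assumption with constant hazard, −ln(0.6)/5 = 0.102 per year. The chance of at least one death among 8 responders is then about 6%, 18% or 34% for a gap of 4, 13 or 26 weeks between assessments. These figures overstate the risk: they apply the mortality of non-responders to responders, and they expose all 8 for the whole gap. The Table 8-1 row for response assessment was not readable in the copy reviewed, so the actual gap is uncertain. The point that the event is probably uncommon stands.

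Two further replies have some weight. The death would not be hidden, since SAP 2.8.2 says "All deaths will be listed and flagged appropriately", and responses are listed too. But the curve and its relapse-free probabilities would still omit it. Also, the rule comes from the protocol, and changing it before the final lock could make the final report differ from earlier ones. Estimates differ only if such a death occurred, however, and in that case showing both estimates settles the matter.

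**Conclusion.** The concern holds. The entry condition conflicts with an endpoint that counts death, and the only event it can remove is a death. If one occurs, relapse-free estimates from that time on are too high: by 10 to 25 points for 10 down to 4 responders when there is no other event, and by 12.5 points for 8. The reported standard error is then also misleading. If none occurs, nothing changes. The conclusion rests on the wording of the rule and on product-limit arithmetic; its practical size depends on an event whose probability the documents do not allow one to estimate reliably. The endpoint is secondary and descriptive and the primary endpoint is unaffected, so this is a minor point.

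**What to change.** Delete the two-assessment condition from SAP 2.7.1. Include every responder, count death as an event on its date, censor any other responder with a single assessment at the date of first response, and report how many subjects are affected. Enter the departure from Protocol 12.5.1 in SAP Section 4, which at present states that there is no change.

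If the sponsor prefers to keep the condition, the SAP should say how assessments are counted, report the number excluded and the reason, and present the all-responder estimate beside the restricted one. If no responder died after a single assessment, a footnote saying so is enough.

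The cost is one sentence removed, two handling rules and one Section 4 entry. No new data are needed and a protocol amendment is not essential. The estimates may come out slightly less favourable.

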## 2 Objectives and endpoints

**Table 2-1 Objectives and related endpoints**

Objective(s)	Endpoint(s)
Primary objective(s)	Endpoint(s) for primary objective(s)

To assess the efficacy of eltrombopag treatment at 6 months in Chinese subjects with a previous diagnosis of severe aplastic anemia and who had insufficient response following at least one treatment course in the period time of > 6 months of immunosuppression with a regimen containing anti-thymocyte globulin (ATG), anti-lymphocyte globulin (ALG), and/or cyclophosphamide, or alemtuzumab, and who are ineligible for HSCT or a suitable donor is not available.

	

Hematologic response rate at 6 months (Week 26) after starting the study treatment defined as the proportion of all subjects who meet any of the IWG criteria in Section 8.3.1.

Secondary objective(s)	Endpoint(s) for secondary objective(s)

To evaluate the efficacy of eltrombopag treatment at 3 months and 1 year

To evaluate the effect of eltrombopag on individual hematologic response (change in neutrophil, platelet, hemoglobin)

To evaluate the time to hematologic response and duration

To evaluate the frequency and volume of transfusion (platelet and RBC)

To evaluate the safety and tolerability of eltrombopag

To determine the pharmacokinetics (PK) of eltrombopag

To evaluate cytogenetic abnormalities, clonal evolution to PNH, evolution to MDS or AML.

	

Hematologic response rate at Week 13 and Week 52

Changes in platelet count (in the absence of platelet transfusion), hemoglobin (in the absence of RBC transfusion) and neutrophil count (in the absence of G-CSF).

Time to hematologic response and duration (any response according to the response criteria for the primary endpoint)

Frequency and volume of transfusion (platelet and RBC)

Frequency/severity of AEs, vital signs, ECG and laboratory abnormalities.

Plasma PK parameters of eltrombopag and trough concentrations

Rate of clonal evolution including clonal evolution to PNH, evolution to AML or MDS.

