For subjects receiving platelet transfusion at baseline, the frequency and the amount of platelets transfusion in each period (Baseline: 4 weeks before Day 1; Week 13, 26, 52: 4 weeks before each visit day) will be summarized. The same analysis applies to RBC transfusion (period will be extended to 8 weeks). The amount of transfusion will be defined as the sum of transfusion multiplied by the volume of transfusion.

The analysis for frequency and amount of transfusion will not be reproduced for final CSR.

Proportion of subjects with transfusion decrease

Subjects with platelet transfusion decrease is defined as subjects with transfusion decrease or transfusion free in each period (Week 13, 26, 52: 4 weeks before each visit day) compared to baseline (Baseline: 4 weeks before Day 1). 50% platelet transfusion reduction is defined as subjects with transfusion decrease of amount (units) at least 50% compared to baseline. The same analysis applies to RBC transfusion (period will be extended to 8 weeks). This analysis will be performed for the subgroup of subjects with baseline transfusion dependent.

The analysis for proportion of subjects with transfusion decrease will not be reproduced for final CSR.

Maximum duration of Platelet and RBC transfusion independence

Transfusion independence duration will be defined as the period from the next day of transfusion to the day before the next transfusion. Maximum duration of platelet and RBC transfusion independence for each subject will be picked for analysis.

Post-baseline transfusion independence will be achieved if subjects who are transfusion dependent at baseline become transfusion free for a period of at least 28 (platelets) or 56 days (RBCs). The time period for assessment of transfusion independence will be at any time during the treatment period. Baseline platelet and RBC transfusion dependence is defined as subjects receiving at least one platelet or RBC transfusion in the 4 weeks and 8 weeks, respectively, prior to the first dose of eltrombopag.

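### The transfusion frequency and amount summary covers only subjects transfused at baseline, so it omits new transfusion starts and leans towards an apparent reduction

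*SAP*

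**What the plan says.** - **Objective and endpoint.** Protocol Table 2-1 states the objective as "To evaluate the frequency and volume of transfusion (platelet and RBC"). Neither the objective nor its endpoint is limited to subjects already receiving transfusions. SAP Table 1-2 repeats both.
- **Planned summary.** SAP 2.7.1, like Protocol 12.5.1, reads "For subjects receiving platelet transfusion at baseline, the frequency and the amount of platelets transfusion in each period". The periods are the 4 weeks before Day 1 and the 4 weeks before the Week 13, 26 and 52 visits. For red cells the SAP adds: "The same analysis applies to RBC transfusion (period will be extended to 8 weeks").
- **Statistics.** Under SAP 2.7.2 the results "will be summarized by descriptive statistics including mean, SD, median, 25th and 75th percentiles, minimum, and maximum".
- **Transfusion decrease (SAP 2.7.1).** "This analysis will be performed for the subgroup of subjects with baseline transfusion dependent".
- **Post-baseline independence (SAP 2.7.1).** "Post-baseline transfusion independence will be achieved if subjects who are transfusion dependent at baseline become transfusion free" for at least 28 days (platelets) or 56 days (RBC), at any time during treatment.
- **Maximum independence duration (SAP 2.7.1).** "Maximum duration of platelet and RBC transfusion independence for each subject will be picked for analysis". SAP 2.7.2 also promises a shift summary from baseline for platelet and RBC independence.
- **Data collected.** Protocol 6.2.1 records RBC transfusions from 8 weeks, and platelet transfusions from 4 weeks, before the first dose to the end of follow-up, for every subject.

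**The concern.** A subject with no transfusion in the baseline window has zero use and can only stay at zero or rise. The rule removes exactly those subjects and keeps the ones who can fall. The plan expects both kinds: SAP 2.2.1 defines subgroups by baseline transfusion independence and dependence. Entry is allowed at platelet counts up to 30 × 10⁹/L (Protocol 5.1), while the platelet transfusion guide is a count below 10 × 10⁹/L or significant bleeding (Protocol 6.2.1.1, 6.2.3). Untransfused entrants are therefore plausible.

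There is a second, separate effect. Subjects are chosen because their baseline count is at least one and are then measured again, so regression to the mean pulls the follow-up value down. The study has one arm (Protocol 4.3), so no control group would show how much of a fall is artefact.

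Less transfusion is one of the benefits claimed in Protocol 4.5.2, and Protocol 1.2 says the results will support registration. A table that favours a reduction by construction is a weak basis for that claim.

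**Working it through.** **Plan's own figures.** The documents give no planning figure for transfusion. Their only planning figures are the 90% Clopper-Pearson intervals for response with n = 20 (Protocol 12.8.1, SAP 3.1). These reproduce: 4/20 (7.1, 40.1), 6/20 (14.0, 50.8), 8/20 (21.7, 60.6), 10/20 (30.2, 69.8), with a largest half-width of 19.8. They are not affected by this point.

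**Step 1: does another planned output count new starts?**

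| Output | Reaches a subject untransfused at baseline? | Counts new need per window? |
|---|---|---|
| Frequency and amount | No | No |
| Transfusion decrease | No | No; counts decreases only |
| Post-baseline independence | No | No |
| Maximum independence duration | Yes | No; takes the longest gap, so later worsening need not show |
| Shift summary | Possibly | Not clearly; no rule for independent-to-dependent |
| Response and duration by lineage | Yes | No; a new transfusion is not separated from too small a rise in count |
| Therapy listings and summaries | Yes | No; no amounts per window and no split by baseline status |

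Overall response needs only one lineage (SAP Table 2-2), so a subject newly needing platelets can still count as a responder through hemoglobin or neutrophils. For an RBC-independent subject with baseline hemoglobin of 90 g/L or more, Table 2-2 has no hemoglobin criterion, so a new RBC need is not even a lineage failure.

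**Step 2: omission, by illustration.** All figures are assumed. Of 20 subjects, 12 are transfused at baseline and fall from 3 to 2 units each; 8 are not and rise from 0 to 1.5.
- Planned table: 12 × 3 = 36 to 12 × 2 = 24, a 33% fall.
- All subjects: 36 + 0 = 36 to 24 + 8 × 1.5 = 36, no change.

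The figures were picked to show the mechanism and do not predict the result.

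**Step 3: selection, with no true change.** Assume each subject's count per window is Poisson with constant mean L.
- Share excluded = exp(−L).
- Baseline mean among those kept = L / (1 − exp(−L)); their follow-up mean = L.
- Spurious fall = 1 − L / [L / (1 − exp(−L))] = exp(−L).
- True rate ratio needed before the restricted mean rises = 1 / (1 − exp(−L)).

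| L per window | Excluded | Baseline mean, kept | Follow-up mean | Spurious fall | Break-even rate ratio |
|---|---|---|---|---|---|
| 0.5 | 61% | 1.27 | 0.5 | 61% | 2.54 |
| 1 | 37% | 1.58 | 1 | 37% | 1.58 |
| 2 | 14% | 2.31 | 2 | 14% | 1.16 |
| 4 | 2% | 4.08 | 4 | 2% | 1.02 |

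**Step 4: subjects who differ in rate.** Let the rate vary as a gamma with mean m and shape k. The spurious fall becomes (k/(k+m))^(k+1). For example, m = 1 and k = 1 give (1/2)² = 25%. Over k = 0.5, 1 and 2 the fall is 35% to 51% at m = 0.5, 19% to 30% at m = 1, 9% to 13% at m = 2, and about 4% at m = 4. The direction is the same throughout, and the fall is smaller than under a common rate except at m = 4, where both are small.

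**The case against.** A reader might infer that subjects who start transfusions vanish from the whole plan. The documents do not support that:
- Transfusions are recorded with concomitant and non-drug therapies (Protocol 6.2.1). These are to be summarised (Protocol 12.3), and all therapies are listed (SAP 2.4.2). With about 20 subjects, new starts can be read from a listing.
- A platelet-independent subject transfused in the 4 weeks before the visit fails the platelet criterion (note to SAP Table 2-2). SAP 2.5.5 reports response by lineage.
- SAP 2.7.1 analyses duration by lineage, so for a lineage responder a new transfusion can end the response.
- Maximum independence duration carries no baseline restriction.

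A reader might also infer that the table can hardly show worsening. That is too strong: if baseline-transfused subjects needed more, the mean, quartiles and maximum in SAP 2.7.2 would show it. The restriction also works by transfusion type, so a subject given only red cells at baseline stays in the RBC table.

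It can further be said that the analysis is descriptive, was already in the protocol, and answers a fair question about subjects who depend on transfusion. All of this stands. It narrows the point without answering it, because none of these outputs clearly gives the number of new starts, or the amount transfused, in each window.

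**Conclusion.** The point holds in a limited form. The endpoint is unrestricted and its analysis is not. As written, the summary leaves out new starts of each transfusion type and is biased towards apparent reduction.

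The direction of the selection effect is firm if an individual's need fluctuates between windows. Its size is not known. It could dominate the table if transfusions average about one or fewer per window, and would be negligible at four or more. That range rests on the assumed Poisson or gamma-Poisson counts with no true change, and concerns means; medians may behave differently. The documents give neither the transfusion rates nor the share of subjects untransfused at entry, so they do not show that a reported reduction would be false. The primary endpoint and its confidence interval are untouched.

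**What to change.** In SAP 2.7.1 and 2.7.2, keep the baseline-transfused table as a labelled subset and add:

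1. Frequency and amount per window for all FAS subjects under observation, separately for platelets and RBC. Enter zero where a subject was observed and received none; do not enter zero for a subject no longer observed.
2. The number and percentage of baseline-independent subjects, by transfusion type, with at least one transfusion in the window before Weeks 13, 26 and 52.
3. A rule for post-baseline dependence, so that the shift summary in SAP 2.7.2 shows moves from independent to dependent as well as the reverse.

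No new data are needed. The cost is SAP wording and a few table rows, and all-subject medians may sit near zero, which is why the subset table should stay beside them. SAP 2.7.1 does not reproduce this analysis for the final CSR, and this SAP version precedes only the final database lock. The additions would therefore be a new final-CSR output and should be labelled as added after the primary and updated analyses.
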